17 CHANGE HISTORY

Version	Change	Author	Date
1.0	Introduction of document	[REDACTED]	December 21, 2016
2.0	
Addition of Windchill number and study title to footer of document.
 
Update to Investigation Schedule to include CM/AE/MH.
 
Update to Medical Monitor details.
 
Rewording of primary and secondary endpoints.
 
Addition of 12 month follow up visit (FUV2).
 
Removal of CANTAB as electronic cognitive test battery and replacement with NIH Toolbox
 
Removal of SF-12, Cohen Social Network Index, and York Hearing Related Quality of Life measures.
 
Addition of Lubben Social Network Scale and EQ-D5
 
Change from CES-D to Geriatric Depression Scale (GDS).
	[REDACTED] [REDACTED]	August 31, 2017
3.0	
Removal of NIH Toolbox and replacement with Cogstate test battery.
 
Updated secondary objectives, endpoints and hypothesis.
 
Updated reference to Statistical Analysis Plan
	[REDACTED] [REDACTED]	October 6, 2017
4.0	Amendment to Data Privacy Section	[REDACTED] [REDACTED]	January 29, 2018
5.0	
Update to short study title to 'Immediate vs Delayed Cochlear Implantation on Hearing Handicap Study'
 
Numbering of inclusion and exclusion criteria.
 
Typo correction for exclusion criteria #7 in synopsis.
 
Clarification of noise type – speech-weighted noise.
	[REDACTED] [REDACTED]	March 9, 2018

Version	Change	Author	Date
6.0	
Assessment of phonemes correct added.
 
Changed primary objective and endpoint to assess Speech, Spatial and Qualities of Hearing (SSQ12) replacing Hearing Handicap Inventory for the Elderly - Screening (HHIE-S).
 
Addition of FUV3 for Arm B subjects to assess outcomes at 12 months post-activation to align with Arm A post-activation follow up.
 
Replacement of Mini Mental State Exam (MMSE) with Montreal Cognitive Assessment (MoCA).
 
Specification of PTA (500, 1000 & 2000 Hz) \geq 70 dB HL in inclusion criteria.
 
Removal of EQ-5D, Lubben Social Network, SPPB, THI questionnaires.
 
Specification of CI532 cochlear implant.
 
Addition of clinical review visits including audibility review at 3 months after POV2.
 
Addition of X-ray preoperatively and CT imaging post-operatively.
 
Removal of pure tone audiometric testing during follow up visits, and requirement for bone conduction testing during screening and baseline visits.
	[REDACTED] [REDACTED]	December 5, 2018
7.0	
Corrected visit window for surgery in Investigation Procedures table.
 
Referred to Statistical Analysis Plan for randomization details.
	[REDACTED] [REDACTED]	December 6, 2018
8.0	
Updated Montreal Cognitive Assessment Scale (MoCA) to utilize the Hearing Impaired version of the Montreal Cognitive Assessment Scale (HI-MoCA) with a supplemental visual presentation of instructions.
 
Included text describing the imaging requirements for the clinical investigation.
	[REDACTED] [REDACTED]	February 1, 2019
9.0	Alignment of tympanometry, demographics and hearing history with EDC System.	[REDACTED] [REDACTED]	March 1, 2019
10.0	Addition of Cochlear Nucleus CI632 cochlear implant with Slim Modiolar electrode and exclusion of protocol deviation for inability to perform tympanometry due to no seal with probe tip.	[REDACTED] [REDACTED]	June 17, 2019
11.0	Addition of subject status language, ACE 27 index for medical history and clarification of hearing history information to be collected and protocol amendment criteria, Consistent addition of Cochlear Nucleus CI632 cochlear implant with Slim Modiolar electrode. Removal of protocol deviation for inability to perform tympanometry and removal of specific medical monitor information.	[REDACTED]	August 16, 2019

18 DEFINITIONS

Term	Description
Adverse event (AE)	
Any untoward medical occurrence, unintended disease or injury, or untoward clinical signs (including abnormal laboratory findings) in subjects, users or other persons whether or not related to the investigational medical device.
 
NOTE 1 This definition includes events related to the investigational medical device or the comparator
 
NOTE 2 This definition includes events related to the procedures involved.
 
NOTE 3 For users and other persons, this definition is restricted to events related to investigational medical devices.

Adverse device effect (ADE)	
Adverse device effect is an adverse event related to the use of an investigational medical device.
 
Note to the author:
 
NOTE 1 This includes any adverse event resulting from insufficiencies or inadequacies in the instructions for use, the deployment, the implantation, the installation, the operation, or any malfunction of the investigational medical device.
 
NOTE 2 This definition includes any event resulting from use error or from intentional misuse of the investigational medical device.

CRF	Case Report Form. A form to facilitate the collection of clinical data during a clinical investigation.
DMC	Data Monitoring Committee
DD	Device Deficiency. A device deficiency is an inadequacy of a medical device with respect to its identity, quality, durability, reliability, safety or performance. Device deficiencies include malfunctions, use errors, and inadequate labelling.
FUV	Follow-Up Visit
Incident	Any malfunction or deterioration in the characteristics and/or performance of a device, as well as any inadequacy in the labelling or the instructions for use which, directly or indirectly, might lead to or might have led to the death of a subject, or USER or of other persons or to a serious deterioration in their state of health.
IC	Informed Consent
IRB	Institutional Review Board
POV	Preoperative Visit

Term	Description
Serious adverse event (SAE)	
A serious adverse event is any adverse event that:
 
 a) led to a death, b) led to a serious deterioration in the health of the subject that either resulted in 
 1) a life-threatening illness or injury, or 2) a permanent impairment of a body structure or a body function, or 3) in-patient hospitalization or prolonged hospitalization, or 4) medical or surgical intervention to prevent life-threatening illness or injury or permanent impairment to a body structure or a body function, c) led to foetal distress, foetal death or a congenital abnormality or birth defect 
NOTE Planned hospitalization for a pre-existing condition, or a procedure required by the CIP, without serious deterioration in health, is not considered a serious adverse event.

Serious adverse device effect (SADE)	A serious adverse device effect is an adverse device effect that has resulted in any of the consequences characteristic of a serious adverse event.
Unanticipated serious adverse device effect (USADE)	An unanticipated serious adverse device effect is a serious adverse device effect which by its nature, incidence, severity or outcome has not been identified in the risk analysis report (for the investigational device or its comparator).

This statistical analysis plan (SAP) describes the planned statistical methods to be used during the reporting and analysis of data collected under the Clinical Investigation Plan CLTD5693, Hearing Loss in Older Adults: Randomized controlled trial of immediate versus delayed cochlear implantation, Version 9.0. This SAP should be read in conjunction with the study clinical investigation plan (CIP) and case report forms (CRFs).

Applicable Documents:

Document Number, Version	Document Title
D1168460, Version 9.0	Clinical Investigation Plan CLTD5693, Hearing Loss in Older Adults: Randomized controlled trial of immediate versus delayed cochlear implantation

2 List of Abbreviations and Definitions of Terms

Abbreviation/Term	Definition
AE	Adverse Event
CI	Cochlear Implantation
CIP	Clinical Investigation Plan
CRF	Case Report Form
Enrolled	Subjects will be enrolled in the study once the inclusion/exclusion criteria are met (including attempted and successful implantation of a device).
ITT	Intent-to-Treat
SAP	Statistical Analysis Plan
Screened	Each subject who signs the study Informed Consent Form will be considered a screened subject.

[figure not shown]
3 Study Objectives

3.1 Primary Objective

To determine the effect of treating hearing loss with cochlear implantation (CI) versus continued use of hearing aids (HA) on hearing satisfaction using the Speech, Spatial and Qualities of Hearing (SSQ12) in older adults.

3.2 Secondary Objective

To assess cognition in older adults with hearing loss with a Cogstate® battery of neuropsychological tests.

Statistical Analysis Plan		Page 7 of 16
Sponsor Cochlear	Study Hearing Loss in Older Adults	CIP Version 9.0

4 Study Design

Prospective, 1:1 randomized controlled trial of immediate versus delayed cochlear implantation (CI) on hearing satisfaction, handicap, communicative function, loneliness, mental wellbeing, quality of life and cognitive functioning. The study will contain approximately 60 subjects, with a minimum of 28 subjects in each arm.

4.1 Randomization

Subjects will be randomized after eligibility has been confirmed and confirmed that the subject will participate in the clinical investigation. Randomization will be performed using a random permuted block design stratified by field site with a 1:1 allocation ratio (Arm A: immediate cochlear implant vs. Arm B: hearing aid control). If a subject withdraws from the clinical investigation, they will be not be replaced by another subject. The randomization table will account for 20% subject attrition.

4.2 Blinding

No blinding will be applied in this study.

[figure not shown]
5 Sample Size Determination.

5.1.1 Primary endpoint

The primary endpoint for the clinical investigation is assessment of the impact of cochlear implantation versus continued hearing aid use on the Speech, Spatial and Qualities of Hearing – short form (SSQ12) test measure at Follow-up Visit 1 (FUV1). Each subject will serve as their own control.

Data from a clinical investigation on the Cognitive Performance of Severely Hearing-impaired Older Adults Before and After Cochlear Implantation (1) was used to estimate the effect of cochlear implantation on the SSQ12.

The sample size estimation for the primary endpoint is based on the mean (SD) change of 3.0 (1.8) for the change in SSQ12 score reported in Claes et al. (pre-operative to postoperatively at six months post-activation) (1). The sample size estimation assumes that the observed mean change and standard deviation of change reported by Claes for SSQ12 is representative of the corresponding values for the clinical population under investigation.

Statistical Analysis Plan		Page 8 of 16
Sponsor Cochlear	Study Hearing Loss in Older Adults	CIP Version 9.0

Sample size calculations were conducted using PASS statistical software under the following general assumptions:

1. Two-sample t-test
2. Two-sided 0.025 α levels
3. 80% power
4. No accounting for attrition or lost to follow up

In order to achieve 80% power with an effect size of 1.667 ($d = (\mu_A - \mu_B)/\sigma$) with 20% attrition, a sample size of 12 per arm would be needed respectively. Therefore, a sample size of 60 supports the effect sizes observed in Claes et al. (2018) as well as possible attrition.

6 Statistical Analyses

6.1 General Considerations

Except where otherwise specified, the following general principles apply to the planned statistical analyses. All statistical analysis will be conducted using SAS version 9.4 or later (SAS Institute Inc., Cary, NC) or other widely-accepted statistical or graphical software as required.

6.1.1 Descriptive Statistics

Continuous data will be summarized with mean, standard deviation, median, minimum, maximum, and number of evaluable observations. Categorical variables will be summarized with frequency counts and percentages. Confidence intervals may be presented, where appropriate, using the t-distribution for continuous data and Clopper-Pearson Exact method for categorical variables.

Statistical Analysis Plan		Page 9 of 16
Sponsor Cochlear	Study Hearing Loss in Older Adults	CIP Version 9.0

6.1.2 Visit Windows

Unless otherwise specified, visit assessments will be analyzed for each analysis time point as described in Sections 6.6 and 6.7.

Each test measure by arm/visit abbreviation is described in the table below.

Where:

A = Arm A, B = Arm B, and x = number of months post-baseline measure.

[figure not shown]
Procedure	Screening POV1	Baseline POV2	FUV1	FUV2	FUV3
HI-MoCA	A0 or B0		A6 or B6	A12 or B12	B18
HHIE-S	A0 or B0		A6 or B6	A12 or B12	B18
Cogstate		A0 or B0	A6 or B6	A12 or B12	B18
SSQ12		A0 or B0	A6 or B6	A12 or B12	B18
UCLA		A0 or B0	A6 or B6	A12 or B12	B18
GDS		A0 or B0	A6 or B6	A12 or B12	B18
LAQ		A0 or B0	A6 or B6	A12 or B12	B18
HUI-III		A0 or B0	A6 or B6	A12 or B12	B18
CNC words		A0 or B0	A6 or B6	A12 or B12	B18
AzBio sentences		A0 or B0	A6 or B6	A12 or B12	B18
Audiometric thresholds	A0 or B0		A6 or B6	A12 or B12	B18

6.1.3 Statistical Significance

Unless otherwise specified, hypothesis testing will be performed at the two-sided 0.05 significance level (or equivalently at a one-sided 0.025 level). P-values will be rounded to three decimal places. If a p-value is less than 0.001 it will be reported as "<0.001". If a p-value is greater than 0.999, it will be reported as ">0.999".

6.1.4 Reporting Precision

Unless otherwise specified, the following conventions will apply for data display. In general, percentages will be displayed to 1 decimal place. Percentages <0.05% will be reported to 2 decimal places. For continuous parameters, means and medians will be reported to 1 additional decimal place than the measured value while standard deviation will be reported to 2 additional decimal places than the measured value. Minimum and maximum values will be reported to the same precision as the measured value.

Statistical Analysis Plan		Page 10 of 16
Sponsor Cochlear	Study Hearing Loss in Older Adults	CIP Version 9.0

6.2 Analysis Populations

The following analysis populations are defined for analysis:

- Enrolled Analysis Set:** The enrolled population will consist of all subjects who signed an informed consent form and have been included into the study database.
- Intention-to-treat Analysis Set:** The intention-to-treat (ITT) population consists of all enrolled subjects who were subsequently randomized. The ITT set will be analyzed according to randomized treatment assignment regardless of adherence to treatment protocol (e.g. dropout/withdrawal or CIP deviations).
- Safety Analysis Set:** The safety population will consist of all ITT subjects who received the device and will be analyzed according to treatment actually received (e.g. this is an as-treated analysis set). If all patients receive study treatment according to randomization, the safety set will be identical to the ITT set.

6.3 Poolability Analyses

All investigational sites will follow the requirements of a common protocol and standardized data collection procedures and forms. The primary endpoints will be presented separately for each site using descriptive statistics. Poolability of the primary endpoints across investigational site will be evaluated using a logistic regression model with fixed effects for treatment, site, and treatment by site interaction.

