9.2.3.5 Speech, Spatial, and Qualities of Hearing Scale (SSQ12)

The SSQ is a validated 12-question self-assessment metric commonly used in hearing research, designed to measure auditory disability across a wide variety of everyday world domains. The SSQ-12 (28) has twelve questions and is derived from the original 49 item SSQ (29). In addition to a reduced administration time, the SSQ-12 has been shown to have similar results to the original 49 item scale (28).

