6.6.1.1 Primary Analysis

The primary efficacy endpoint will be assessed with the following hypothesis:

$$H_0: \mu_A \geq \mu_B$$

$$H_a: \mu_A < \mu_B$$

Statistical Analysis Plan		Page 11 of 16
Sponsor Cochlear	Study Hearing Loss in Older Adults	CIP Version 9.0

Where μ_{A6} is the mean SSQ12 score for the cochlear implantation treatment Arm A and μ_{B6} is the mean SSQ12 score for the hearing aid control Arm B at FUV1. The hypothesis will be evaluated using a regression model with treatment and baseline score as covariates. Significance of the treatment effect will be assessed by the p-value for the treatment arm from the regression model.

For analyses using means in the primary endpoints, where there is evidence the model assumptions are not met (e.g. lack of normality of the residuals), transformations or non-parametric tests will be employed.

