6.7.1.2 Tertiary Analyses

All tertiary analyses will be presented using descriptive statistics and analyzed using a t-test to compare the mean score of the cochlear implant Arm A to that of the hearing aid control Arm B at various time points. As these tertiary analyses are exploratory in nature, there will be no adjustment for multiple comparisons, no formal hypotheses testing and no statement of statistical significance.

Investigating treatment effect on:

- Neuropsychological outcomes:
 - Cogstate¹:
 - ☒ Detection Test – speed of performance
 - ☒ Groton Maze Learning Test – number of errors
 - ☒ Identification Test – speed of performance
 - ☒ One Card Learning Test – accuracy of performance
 - ☒ One Back Test – speed of performance
 - A6 vs B6 (treatment effect)
 - A0 vs B0 (population)
 - A6 vs B12 (6 months post-CI)
 - A12 vs B18 (12 months post-CI)
 - A0 vs A6 vs A12 (longitudinal treatment effect)
 - B6 vs B12 vs B18 (longitudinal treatment effect)
 - HI-MoCA:
 - ☒ A6 vs B6 (treatment effect)
 - ☒ A0 vs B0 (population)
 - ☒ A6 vs B12 (6 months post-CI)

¹ A sensitivity analyses will be conducted with test data integrity failures excluded if the integrity failure rate is greater than 10%.

Statistical Analysis Plan		Page 13 of 16
Sponsor	Study	CIP Version
Cochlear	Hearing Loss in Older Adults	9.0

- ☒ A12 vs B18 (12 months post-CI)
- ☒ A0 vs A6 vs A12 (longitudinal treatment effect)
- ☒ B6 vs B12 vs B18 (longitudinal treatment effect)
- Psychosocial measures:
 - UCLA Loneliness Scale:
 - ☒ A0 vs B0 (population)
 - ☒ A6 vs B12 (6 months post-CI)
 - ☒ A12 vs B18 (12 months post-CI)
 - ☒ A0 vs A6 vs A12 (longitudinal treatment effect)
 - ☒ B6 vs B12 vs B18 (longitudinal treatment effect)
 - Geriatric Depression Scale (GDS):
 - ☒ A0 vs B0 (population)
 - ☒ A6 vs B12 (6 months post-CI)
 - ☒ A12 vs B18 (12 months post-CI)
 - ☒ A0 vs A6 vs A12 (longitudinal treatment effect)
 - ☒ B6 vs B12 vs B18 (longitudinal treatment effect)
- Audiometric measures:
 - HHIE-S:
 - ☒ A0 vs B0 (population)
 - ☒ A6 vs B12 (6 months post-CI)
 - ☒ A12 vs B18 (12 months post-CI)
 - ☒ A0 vs A6 vs A12 (longitudinal treatment effect)
 - ☒ B6 vs B12 vs B18 (longitudinal treatment effect)
 - SSQ12:
 - ☒ A0 vs B0 (population)
 - ☒ A6 vs B12 (6 months post-CI)
 - ☒ A12 vs B18 (12 months post-CI)
 - ☒ A0 vs A6 vs A12 (longitudinal treatment effect)
 - ☒ B6 vs B12 vs B18 (longitudinal treatment effect)

Statistical Analysis Plan		Page 14 of 16

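### SAP 6.3 checks poolability of SSQ12, a score analysed as a mean, with a logistic model; separately, site, the randomisation stratum, is in neither the primary nor the imputation model

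*SAP*

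**What the plan says.** **Poolability (SAP 6.3).** The section has two parts. The first is descriptive: "The primary endpoints will be presented separately for each site using descriptive statistics". The second is a model, to be fitted "using a logistic regression model with fixed effects for treatment, site, and treatment by site interaction". The section gives no significance level, no cut-off and no action to follow from the result.

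**The endpoint.** SAP 6.6.1 names one primary efficacy endpoint, SSQ12 at FUV1, Arm A against Arm B. It is treated as a continuous score throughout:

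- Sample size (SAP 5.1.1): a two-sample t-test based on a "mean (SD) change of 3.0 (1.8) for the change in SSQ12 score".
- Primary analysis (SAP 6.6.1.1): the Arm A parameter "is the mean SSQ12 score for the cochlear implantation treatment Arm A", and the comparison is made "using a regression model with treatment and baseline score as covariates". The fallback for failed model assumptions opens "For analyses using means in the primary endpoints".
- Tertiary SSQ12 comparisons (SAP 6.7.1.2): "analyzed using a t-test to compare the mean score of the cochlear implant Arm A".
- Instrument (Protocol 9.2.3.5): a "validated 12-question self-assessment metric commonly used in hearing research", with no responder definition or categories.

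**Site.** SAP 4.1 randomises 1:1 in permuted blocks within field site. The primary model contains treatment and baseline only. SAP 6.4 lists baseline, age and gender for the multiple imputation of SSQ12. The only model that contains site is the one in 6.3.

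**The concern.** A logistic model needs a binary or ordered outcome, and the plan gives none for SSQ12. Whoever runs 6.3 must either choose a cut-off, in a trial without blinding (SAP 4.2), or choose a cumulative-logit model that treats the score as ordered. The second needs no cut-off, but the plan does not name it, and its interaction is on the odds-ratio scale rather than the mean difference that the primary analysis reports. The site-consistency analysis is therefore not determined by the plan.

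The site omission is a separate matter. Stratified randomisation removes between-site variation from the treatment comparison. A model without site leaves that variation in the residual, so the model standard error can exceed the true one. What is at stake is some precision and an interval wider than it need be.

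**Working it through.** **1. The plan's own figure.** Inputs from SAP 5.1.1: difference 3.0, SD 1.8, two-sided alpha 0.025, 80% power, 20% attrition. d = 3.0/1.8 = 1.667. By the noncentral t, 9 per arm gives 84.4% power, and 9/(1 − 0.20) = 11.25, rounded up to 12 per arm. The stated 12 reproduces, with SSQ12 as a continuous score. At the same d and alpha, 24 per arm (60 randomised, 20% lost) gives 99.96% power.

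**2. Logistic model set against the endpoint.** Sections 5.1.1, 6.6.1.1 and 6.7.1.2 use means. Section 6.3 uses a logistic model. The fallback in 6.6.1.1 is to transform or to go non-parametric, which supplies no categories.

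**3. Illustration only: what dichotomising would do.** The SAP does not propose a dichotomised analysis, and the number of sites is assumed. Take arm means 0 and 3.0, SD 1.8 and a cut at the midpoint 1.5, the most favourable cut. The chance of falling on the expected side is p = Φ(1.5/1.8) = 0.798 in each arm. The chance that at least one arm-by-site cell is all 0 or all 1 is 1 − Π[1 − pⁿ − (1 − p)ⁿ]. For 6 equal sites (12 cells of 5): pⁿ = 0.323, (1 − p)ⁿ = 0.0003, so 1 − 0.677¹² = 0.991.

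| Equal sites | 60 subjects | 48 completers | 60 subjects, no effect |
|---|---|---|---|
| 4 | 81% | 91% | 9% |
| 6 | 99% | 99.8% | 54% |
| 10 | >99.9% | >99.9% | 99.7% |

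Some interaction coefficients, not necessarily all, would then be non-finite.

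**4. The linear alternative for 6.3.** Simulation, 4,000 trials, 20% dropout, effect 3.0; 4, 6 and 10 equal sites. Every arm-by-site cell has data in 100%, 99% and 78% of trials. The interaction F-test has type I error 4.8–5.0%. Its power for a between-site SD of the effect of 1.0 point is 29.2%, 24.5% and 18.4%. It is valid but weak.

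**5. Leaving site out of the primary model.** Simulation, 10,000 trials per setting, 60 randomised, blocks of 4 within site, baseline correlation 0.5, no dropout, complete cases. ICC means the share of variance beyond baseline that is due to site. Nominal level 5%.

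| Sites | ICC 0.05, no site | ICC 0.10, no site | ICC 0.20, no site | ICC 0.20, site unpooled |
|---|---|---|---|---|
| 4 | 4.39% | 4.02% | 3.31% | 4.90% |
| 6 | 4.11% | 4.55% | 3.26% | 4.98% |
| 10 | 4.61% | 4.23% | 3.42% | 5.40% |

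If site acts only through baseline, the level without site is 4.76–4.94%. At ICC 0.20 the model and true standard errors, in points, are 0.405 v 0.370, 0.409 v 0.373 and 0.414 v 0.380, a ratio of 1.09 to 1.10. Cross-check: 1.96 × 1.095 = 2.15, whose two-sided normal tail is 3.2%.

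**6. The small-site rule.** Power at an assumed 1.2-point effect, 20% dropout, 10 sites of 6, where sites below the cut-off form one level:

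| | Cut-off 4 or 6 (sites kept separate) | Cut-off 8 (all pooled = current model) | Difference |
|---|---|---|---|
| ICC 0.20 | 76.2% | 72.6% | +3.6 points |
| ICC 0 | 68.6% | 72.4% | −3.8 points |

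Pooling also limits the correction of the level. With a cut-off of 8 at ICC 0.20, no dropout, type I error is 3.4% with 10 equal sites (unchanged), 4.3% in a 15-site unequal layout and 4.7% in a 10-site unequal layout.

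**7. Imputation.** With 20% random dropout, and if the three listed covariates are the whole imputation model, a true 3.0 is estimated as 2.37–2.38. The rough arithmetic is 3.0 × (1 − 0.20) = 2.4, because imputed values carry no arm difference. With site but not arm it is 2.31–2.34; with both, 2.99–3.00. Power at 3.0 points is at least 99.4% in every option.

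**The case against.** The strongest reply is that nothing important turns on this. Section 6.3 triggers no decision, and its plural reference to primary endpoints, when there is only one, suggests carried-over template wording. The by-site descriptives stand. The corrected interaction test has at most 29% power in the settings tried, so it adds little to them. The primary model with treatment and baseline is pre-specified and valid, and it errs on the safe side. Any gain from adding site needs an ICC and a 1.2-point effect (40% of the planned 3.0) that the documents do not contain.

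Most of this stands, and it sets the severity. It does not rescue the logistic wording, because a pre-specified analysis should say which model is to be fitted.

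Some stronger readings are tempting, and the documents do not support them:

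- *That the primary result depends on a poolability test that cannot be run.* 6.3 gates nothing, and a cumulative-logit model could be fitted without a cut-off.
- *That a dichotomised SSQ12 analysis is planned and would fail.* Neither document proposes one. The separation figures only illustrate the consequence of that choice.
- *That ignoring the stratum biases the estimate or inflates type I error.* The effect runs in the conservative direction.
- *That the pooling cut-off is a detail.* With 10 sites of 6 it moves power by about 4 points in either direction.
- *That the attenuation to about 2.4 adds weight here.* It comes from arm being absent from the imputation covariates, a separate issue, and it holds only if the list in 6.4 is complete.

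**Conclusion.** The mismatch in SAP 6.3 is certain from the text: a logistic model is named for a score that is sized and analysed as a mean, with no categories defined in either document. Its consequence is confined to a supporting analysis.

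The absence of site from 6.6.1.1 and 6.4 is also certain. Its size is not, because neither the number of sites nor the between-site variance is stated. At an assumed ICC of 0.20 the nominal 5% test runs at about 3 to 4%, and the model standard error is about 9–10% too large in the no-dropout runs. At ICC 0.05 to 0.10 the level is 4.0–4.6%. If site matters only through baseline, there is no material effect. With power of 99.4% or more at the planned 3.0 points in every option, the primary conclusion would not change. Low severity: worth correcting before analysis, with no threat to the trial's main inference.

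**What to change.** All changes are SAP wording, by the amendment route in SAP section 7, and need no new data.

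1. **SAP 6.3.** Replace the logistic model with a linear regression of FUV1 SSQ12 on baseline SSQ12, treatment, site and treatment-by-site, fitted to sites with FUV1 data in both arms. Keep the by-site descriptive statistics, because the interaction test has low power and some sites may not qualify for the model.
2. **SAP 6.6.1.1.** Add site as a factor, with a rule for pooling small sites fixed before analysis. Choose the cut-off from the actual site sizes, blind to outcome. A high cut-off can return the current model unchanged. A low one costs power if sites do not differ (about 4 points with 10 sites of 6, at the assumed 1.2-point effect) and gains about as much at ICC 0.20.
3. **SAP 6.4.** If site is added to the imputation model, use the same site levels and include treatment arm as well. Site without arm is not enough. Whether arm is already meant to be in that model should be settled as a point of its own.
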